### 4. Sample size and power calculation

We plan to recruit and randomize 350 participants over 24 months. There should be 99% or more power to determine the direct effect of RIMO on the primary outcome of time to MAT initiation (H1a) assuming a sample size of 350 patients, randomized into two groups of 175 each, interviews at 4 time points for the main analysis (baseline, and 3, 6, and 9 months post-randomization), our average completion rate of 94+% per follow-up wave, and a moderate to large effect size of  $d=3.0$ . This expected effect size was based on the natural log of the odds ratio ( $\text{Log}^e(\text{OR})=d$ ) of initiating MAT ( $\text{OR}=20.2$ ) from RIMO Pilot study ([name] et al., under review). For the other tests of direct effects, the effective n for power calculations in repeated measures analysis varies between a lower bound of the number of unique people per group ( $N=175$  people), and an upper bound of the number of people randomized plus the completed follow-up interviews or 668 observations per group ( $O=(175 \text{ people at intake} + \text{average of } 94\% \times 175 \text{ people} \times 3 \text{ follow-ups})$ ) as a function of the intra-class correlation coefficient (ICC) associated with the individual and the number of repeated measures (RM) per person ( $\text{effective } n'=O/(1+\text{ICC}(\text{RM}-1))$ ). In our prior studies, ICC of the other dependent

variables ranged from .13 to .34. Thus the effective n= range from 429 to 398 per group and be capable of detecting an effect size of  $d=0.2$  or more with 80% power for a two-tailed test of  $p<.05$  of effect sizes  $d=.2$  or more. For mediation analysis, the tests should also have 80%+ power for a 2-tailed test of  $p<.05$  and an indirect effect size of  $d=.2$  or more.

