## **10. Statistical analysis plan**

Missing data. Participants will complete their baseline interview prior to randomization. Based on prior studies conducted by the applicants, it is expected that approximately 90% or more of the 3, 6, and 9-month post-randomization interviews will be completed. Among these completed interviews, prior studies conducted by the team indicate that less than 1% will have additional missing data on any of the core items required to test the study hypotheses. Multiple imputations will be used to replace the small amounts of missing data to allow the least biased estimate for each analysis. To further reduce potential bias, analyses will be rechecked by running them without missing data. If there are any clinically significant differences ( $d > |.2|$ ), a general latent variable framework will be used to analyze non-ignorable or systematic missing data that tests whether missing data is qualitatively different by condition.

Survival Analysis for Time to MAT Initiation and Time on Medication (Aim 1). The primary outcome is the days from randomization until the initiation of any kind of MAT. Relative to the referral only control group, the direct effects of RIMO on reducing the days from randomization to initiation of any MAT (H1a) and increasing the days on medication after initiation (H1b) will be evaluated with a Cox Regression model using IBM SPSS version 24 with random assignment to RIMO as the main predictor, as the investigators have done in earlier experiments. It will be examined after the point of randomization and after each follow-up interview. Survival analysis incorporates information about censorship (e.g., death, people who were not admitted to MAT within 9 months) and can incorporate covariates if needed. The output includes a case summary (e.g., missing data, other problems, descriptive statistics) and an evaluation of each term (e.g., beta, its standard error, Wald, its probability, the odds ratio, the 95% confidence interval for the odds ratio). The beta can also be converted to a Cohen's effect size *d*. All analyses will use an intent-to-treat approach (i.e., participants are analyzed as assigned regardless of their actual level of participation in RIMO). We will also conduct a secondary analysis of the time to MAT initiation after each RIMO checkup to understand the pattern over time as we have done with earlier experiments.

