Direct Effects of RIMO on MAT (Aim 1). Relative to the referral only control group, the direct effects of RIMO on reducing dropout and receiving more total days of MAT will be evaluated using a multilevel structural equation modeling (MSEM) with mixed effects in MPlus (version 7.4). The analysis will model observations (Level 1) nested within participants (Level 2), with participants modeled as a random factor anchored on the baseline version of the dependent variable. Randomization to RIMO will be modeled as a Level 1 predictor. We will check for the need to use models that adjust for counts or zero saturation.

Direct Effects of RIMO on Secondary Outcomes of Time to Relapse, Opioid Use and Overdose (Aim 2) and Death, OUD, Health, Mental Health, and Health Care Utilization (Aim 3). Relative to the referral only control group, the direct effects of RIMO on time to first relapse (H2) will be evaluated with a survival analysis similar to Aim 1 H1. It will be examined after the point of randomization and after each follow-up interview. The direct effects of RIMO on days of opioid use (H2), opioid overdoses (H2), opioid-related fatality (H3), symptoms of OUD (H3), physical health problems (H3), mental health symptoms (H3), and the cost of health care utilization (H3) will also be evaluated using a series of MSEM with mixed effects in MPlus modeled in the same way as above. Most of the above variables are relatively continuous, but we will check for the need to use models that adjust for counts or zero saturation. For opioid-related fatality (H3), we will define the dependent variable as dichotomous in MPlus (equivalent to using logistic regression).

Indirect Effects of RIMO (Aims 2 and 3). To evaluate indirect effects, we will determine the extent to which the direct effects of RIMO on the above dependent variables are changed by of days of MAT received (H2 & H3) and/or days of opioid use (H3) using the Preacher and colleagues framework for testing mediation in MSEM with REML in MPlus. Loss of statistical significance in the path coefficient from the intervention conditions to the other outcome variables would indicate full mediation; a reduction in the path coefficient would indicate partial mediation. Change will be evaluated using MacKinnon's joint-significance testing of the path *z*-scores with a Sobel test using a standard error based on bootstrapping and criteria of  $p < .05$  on the degree of change.

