#### **20. Trial stopping rules**

The primary stopping rule would be based on a statistically significant ( $p < .05$ ) and clinically significant ( $d < -0.2$ ) finding in the wrong direction (i.e., experimental group doing worse than the control group) on the primary outcome, substance frequency scale. In consultation with the DSM monitor, the trial could also be stopped (or modified) if other unexpected issues come up suggesting that the intervention or research procedures are causing harm.

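### Calling mediation full when the RIMO path loses significance treats a non-significant direct effect as zero

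*Combined protocol and SAP*

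**What the plan says.** Section 10, under indirect effects for Aims 2 and 3, asks how far RIMO's effects on the outcomes change once days of MAT (H2, H3) and days of opioid use (H3) are taken into account. It gives two labelling rules. The first is "Loss of statistical significance in the path coefficient from the intervention conditions to the other outcome variables would indicate full mediation". The second is that "a reduction in the path coefficient would indicate partial mediation". The change is then tested by joint significance of the paths "with a Sobel test using a standard error based on bootstrapping", at p<.05.

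Section 4 gives the precision behind these tests. It states "Thus the effective n= range from 429 to 398 per group" and 80% power for d=0.2. It adds "For mediation analysis, the tests should also have 80%+ power for a 2-tailed test of" p<.05 "and an indirect effect size of" d=0.2 or more.

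The plan attaches clinical significance to d=0.2 in two other places. In the missing-data paragraph of section 10, a further model is triggered "If there are any clinically significant differences" beyond d=0.2 in absolute value. Section 20 bases stopping on a statistically and "clinically significant ( $d < -0.2$ ) finding in the wrong direction".

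**The concern.** A path that loses significance is usually reduced as well, so under these rules only a p-value separates full from partial mediation. That p-value depends on sample size as much as on the size of the remaining effect. When the direct and indirect effects run the same way, the remaining direct effect is only part of the total, so it is often smaller than anything the trial was sized to detect.

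The test of change does not repair this. It can show that an indirect effect exists, but it says nothing about whether the remaining direct effect is zero or negligible. No section sets a margin, an interval rule or a proportion mediated for that path.

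H2 and H3 each predict direct and indirect effects. A report that follows the rule could say that RIMO acts entirely through MAT days or opioid-use days when a real direct effect remained and was missed for lack of power.

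**Working it through.** **The plan's own power figure.** For a two-group comparison, power ≈ Φ(d·√(n/2) − 1.96).
- n=398, d=0.2: 0.2×√199 = 2.82; Φ(0.86) = 80.5%.
- n=429, d=0.2: 83.4%.

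So 80% holds at the stated effective n. That n does not follow from section 4's formula, O/(1+ICC(RM−1)). With O = 175 + 0.94×175×3 = 668.5 and four time points:
- ICC .13: 668.5/1.39 = 481.
- ICC .34: 668.5/2.02 = 331.

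Both ranges are carried below. Table 2.1 defines MAT days and opioid days as 9-month totals or sums, one value per person, so n=175 is shown too.

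**Power for a smaller remaining effect.** For d=0.1 the same formula gives 29% at n=398, 25% at 331 and 15% at 175. This is a simple two-group test; putting a mediator that differs by arm into the model changes the standard error, as follows.

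**What a just non-significant direct path leaves open.** Let a be the RIMO effect on the mediator in SD, and b = indirect effect/a the mediator-to-outcome path, with within-group SDs of 1. Then

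SE(direct) = √[(1−b²)(2/n)(1+a²/4)].

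An estimate at the edge of significance has a 95% interval from about 0 to 2×1.96×SE. For an indirect effect of d=0.2:

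| a | b | upper limit, n=398 | upper limit, n=175 |
|---|---|---|---|
| 0.3 | 0.67 | 0.21 | 0.32 |
| 0.5 | 0.40 | 0.26 | 0.40 |
| 0.7 | 0.29 | 0.28 | 0.43 |
| 1.0 | 0.20 | 0.30 | 0.46 |

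The documents do not give a. It was extended to 1.0 because the pilot's p<.05 for MAT days, with 16 and 17 participants, implies d of at least 0.71 if it came from a t-test (an assumption).

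**How often the label would be wrong.** Trials were simulated from M = aX + e, Y = c′X + bM + e, with the four values of a above. The table gives the share with a non-significant direct path among trials with a significant total effect; the range runs over a.

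| Scenario | n per group | Called full |
|---|---|---|
| Indirect 0.2, direct 0.2 | 398 | 4–27% |
| Indirect 0.2, direct 0.15 | 398 | 20–51% |
| Indirect 0.2, direct 0.1 | 398 | 53–75% |
| Total 0.2, half mediated | 398 | 61–70% |
| Total 0.2, a quarter mediated | 398 | 30–41% |
| Total 0.2, half mediated | 331–481 | 57–71% |
| Total 0.4, half mediated | 331–481 | 2–35% |
| Total 0.2, half mediated | 175 | 65–72% |
| Total 0.4, half mediated | 175 | 28–59% |

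Also requiring joint significance of the two mediator paths does not lower the shares. For total d=0.2, half mediated, n=398, the range becomes 61–76%.

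**The case against.** - **The d=0.2 threshold is borrowed.** It comes from a missing-data check and a stopping rule for harm, and neither defines a negligible direct path. This stands: 0.2 is a benchmark from elsewhere in the plan. The flaw in the rule does not depend on it.
- **The largest shares belong to small effects.** At n=398 the shares above one half mostly arise when the remaining direct effect is d=0.1. At d=0.2 the rule avoids the wrong label in 73–96% of trials with a significant total effect. The upper limits tabulated are the edge case: with a=0.3 only about 14–26% of results called full have an upper limit above 0.2, though with a of 0.5 to 1.0 most do (about 55–90%). This stands as a limit on size.
- **The word direct is ambiguous.** Section 10 first estimates direct effects in models described without a mediator, so H2 and H3 may mean the total effect, and full mediation would then not contradict them. That weakens the link to the hypotheses. It does not make a non-significant path a zero path.
- **The models are simplified.** Survival, dichotomous, count and two-mediator models are planned and were not simulated. The figures are illustrations; the reasoning carries over.
- **Part of the remedy is planned.** A bootstrap standard error for the indirect effect is already specified. An interval for the remaining direct path is not.

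**Conclusion.** The concern holds. The rule as written can yield a claim of full mediation that the data do not support, and nothing else in the plan prevents it. At the plan's 398 per group and its minimum indirect effect of d=0.2, the wrong label would be given in 4–27% of trials with a significant total effect if a direct effect as large as d=0.2 remains, and in more than half if d=0.1 remains. With one value per person (175 per group), the first range rises to 28–59%.

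These figures rest on a linear, normal, single-mediator model and on path sizes and mediated shares that the documents do not give. The consequence is one of interpretation for secondary aims. H1a, the sample size, the separate tests of RIMO's effects, the test of the indirect effect and the stopping rule do not use the label.

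**What to change.** Delete the sentence in section 10 that defines full and partial mediation. For each outcome and mediator, report the indirect effect with a bootstrap 95% confidence interval and the remaining direct effect with its own 95% interval. State that a non-significant direct path will not be described as full mediation. Keep the joint-significance and Sobel test as the test that an indirect effect exists.

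If the word full is to be kept, set a margin for a negligible direct effect in the SAP beforehand and require the 95% interval of the direct path to lie inside it. This option has a price. With a margin of 0.2 (assumed), a truly fully mediated indirect effect of d=0.2 would earn the label in about 53–95% of trials with a significant total effect at n=398. At n=175 it would do so in about 37% with a=0.3 and 0–3% with a of 0.5 to 1.0. Deleting the label is simpler.

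The cost is SAP wording: no extra data or participants, and for the linear models both estimates come from the fits already planned. For time to relapse and fatality the SAP should also say on what scale the two effects are reported. Readers get two intervals in place of a one-word label.

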**Aim 1: Evaluate RIMO's direct effect on linkage to MAT, length of time on MAT, dropout, and total days of MAT.**

H1: Relative to the control group, RIMO will have a direct effect on: a) initiating MAT sooner, b) staying on medication longer, c) reducing dropout, and d) receiving more total days of MAT.

**Aim 2: Evaluate RIMO's direct and indirect (via MAT) effects on time to relapse, opioid use, and opioid-related overdose.**

H2: RIMO will have direct and indirect (via days of MAT treatment) effects on: a) time to relapse, b) days of opioid use, and c) number of overdoses.

**Aim 3: RIMO's direct and indirect (via MAT and opioid use) effects on opioid-related fatalities, OUD symptoms, physical health, mental health and the cost of health care utilization.**

H3: RIMO will have direct and indirect (via days of MAT treatment and days of opioid use) effects on: a) opioid-related fatalities, b) opioid use disorders symptoms, c) physical health, d) mental health, and e) cost of health care utilization.

Referral Only Control. During the phase 1 pilot, we collaborated with our study partners as well as the Illinois Opioid STR partners to develop a brochure that includes a list of MAT providers in Chicago, and their location, telephone number, hours of operation, adjacent bus lines, and type of funding accepted (e.g., Medicaid). In addition, the brochure includes a range of other SUD treatment options (e.g., residential or outpatient drug-free treatment), including office-based physicians who prescribe buprenorphine or other forms of MAT. This brochure is will be given to participants in both groups at the baseline assessment. Research staff will follow a script that does not include any statements regarding motivation for treatment. At present, based on our interviews with key informants and focus group with pilot study participants, there is currently no systematic method in place for referring individuals to MAT (or other SUD treatment) either from the first responders following administration of naloxone or at the EDs following their admission for opioid-related overdose. Hence, this condition represents more than the “usual care” in the community.

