The first responders will follow their standard practices for obtaining contact information from individuals following naloxone administration (i.e., name, address, phone number). For those who are alert and oriented, first responders will ask one additional question of the participants, which is whether they are willing to be contacted by someone in a few days to see how they are doing and talk about available help. If they respond affirmatively, first responders will request their signature on a form indicating their consent to share their contact information with the study investigators who will contact them, optimally within 48-72 hours. Finally, all individuals, whether or not they consent to release their information, will be provided with a brochure listing MAT providers in the local community. Research staff will pick up the release and contact forms daily from each participating firehouse and police station and document the number of people who overdosed and received naloxone and who: a) agreed, b) were not alert and/or oriented and were not asked, or c) refused. The rate of consent/refusals will be monitored against the total number of daily naloxone administrations. We will look for patterns to consent/refusal and debrief with first responders about the process. Study partners will meet every other week during the recruitment phase to monitor recruitment, discuss challenges, and develop strategies to increase recruitment, if needed. Based on the research team's success on prior studies tracking and locating participants, we expect that research staff will successfully contact approximately 75% of participants by telephone or through direct outreach. As reported in the initial focus group, we expect that almost all will currently be using opioids or heroin. Upon contact, research staff will screen individuals for eligibility based on study inclusion criteria; if eligible, they will be invited to the research office to complete the informed consent and baseline interview and will be randomized. Transportation will be provided as needed.

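### No survival mediation model is stated for time to relapse (H2a), and the coefficient-reduction rule, if read on the Cox scale, understates the mediated share

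*Combined protocol and SAP*

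**What the plan says.** H2 in the summary of the protocol makes time to relapse a mediated outcome: "RIMO will have direct and indirect (via days of MAT treatment) effects on: a) time to relapse". Section 10 then says that "time to first relapse (H2) will be evaluated with a survival analysis similar to Aim 1 H1", and the Aim 1 analysis it points to is "evaluated with a Cox Regression model using IBM SPSS version 24".

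The paragraph on indirect effects covers all the preceding dependent variables at once and uses the Preacher and colleagues "framework for testing mediation in MSEM with REML in MPlus". Loss of significance of the RIMO path is to be read as full mediation, and "a reduction in the path coefficient would indicate partial mediation". The change is to be evaluated by "joint-significance testing of the path" z-scores together with a Sobel test whose standard error is bootstrapped, at p < .05. No separate rule, scale or model is given for time to relapse.

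Table 2.1 defines relapse as the first opioid or heroin use after randomization. No nine-month relapse rate is given. The nearest statement, in section 8, concerns first contact: "we expect that almost all will currently be using opioids or heroin".

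**The concern.** In a linear model, the fall in the treatment coefficient when a mediator is added equals the product of the two mediation paths, so the fall measures the indirect effect. Hazard ratios do not behave this way because they are non-collapsible. A Cox coefficient that leaves out a predictor of the event is pulled toward zero, and adding that predictor moves it away from zero even when nothing is mediated. For a mediator that predicts relapse given arm, this shift works against the drop due to mediation, and it grows with the proportion who relapse.

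The question at stake is the one H2a asks: how much of any delay in relapse runs through MAT days. If the rule is read on Cox coefficients, the reported share is too small when direct and indirect effects have the same sign. In some settings no reduction appears although mediation is real.

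**Working it through.** **Inputs.** From the documents: 175 per arm (section 4) and nine months of follow-up, taken as 270 days. Not in the documents, so assumed over a range: the relapse proportion and three path sizes. These are *a* (effect of RIMO on MAT days, in SD), *b* (log hazard ratio of relapse per SD of MAT days, given arm) and *c'* (RIMO's log hazard ratio given MAT days). *c* is RIMO's log hazard ratio without MAT days. The plan gives no figure for this rule to reproduce; section 4 claims 80% power or more for an indirect effect of d = .2 but gives no path values.

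**Step 1: formulas.** True mediated share = ab/(ab + c'). Share read by the rule = (c - c')/c, both coefficients from Cox fits. For a = .3, b = -.5, c' = -.4, the true share is .15/.55 = 27%. One large simulated data set gave c = -0.460 and c' = -0.393, so the share read is .067/.460 = 15%.

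**Step 2: large-sample simulation.** Exponential relapse times with hazard 0.02·exp(c'X + bM), M = aX + standard normal error, censored at 270 days; 89-98% relapse. Independent runs agreed to within about 3 points.

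| a, b, c' | True share | Share read | Gap (points) |
|---|---|---|---|
| .3, -.5, -.4 | 27% | 14% | 13 |
| .3, -1, -.4 | 43% | 14% | 29 |
| .2, -.8, -.4 | 29% | 0% | 29 |
| .7, -.5, -.4 | 47% | 37% | 10 |
| 1, -.5, -.4 | 56% | 47% | 9 |
| .7, -.3, -.2 | 51% | 46-49% | 2-5 |
| .7 or 1, with c' = 0 | 100% | 97-101% | about 0 |

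With a = 0 and c' = -.4 (no mediation), adding the mediator makes the coefficient grow by about 20% (b = -.5) or 54% (b = -1). With b = 0 and c' = -.5 there is no shift: both fits give -0.500.

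**Step 3: dependence on the event rate.** At 11-15% events the first three rows read 27.5%, 37% and 24%, against 27%, 43% and 29%. In a separate simulation with a = .5 and c' = -.5, the Cox drop as a fraction of ab was:

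| | 10% events | 50% | 95% |
|---|---|---|---|
| b = -.5 | 0.96 | 0.79 | 0.56 |
| b = -1 | 0.87 | 0.54 | 0.30 |

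**Step 4: what is lost at 175 per arm, 95% events, c' = -.5 (600 replicates).**

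| a, b | Power, joint significance of a and b | Power, test on the Cox drop |
|---|---|---|
| .5, -.5 | 1.00 | 0.59 |
| .3, -.5 | 0.80 | 0.12 |

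For a = .2, b = -1, a reduction of any size appears in only 31% of trials.

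The full-mediation label has a further weakness that is about power, not scale. With a = .5, b = -.5, c' = -.2, the true share is .25/.45 = 56%, yet RIMO's coefficient loses significance in 54% of trials.

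**Step 5: an alternative scale.** Over five settings at 95% events, the coefficient drop divided by the product of paths was 0.98-0.99 in a log-normal accelerated failure time (AFT) model, 0.77-0.96 in a Weibull one and -0.29 to 0.74 in Cox.

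**Step 6: Sobel.** With the closed-form standard error, z = z_a·z_b/√(z_a² + z_b²), which is below the smaller path z. If both were 2.5, z = 6.25/3.54 = 1.77, so joint significance passes and Sobel does not. At N = 329, simulated power was about 56% (Sobel) against 74% (joint) for paths .4 and .15, and 72% against 77% for .6 and .15.

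**The case against.** A reader might infer that the plan would miss real mediation of relapse altogether. The documents do not support that. The coefficient rule is not the only criterion: section 10 also calls for joint significance of the path z-scores, which uses *a* and *b* and not the drop. Step 4 shows that it keeps its power under Cox.

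A reader might also infer that any added covariate distorts the coefficient. It does not; the variable must predict relapse given arm. H2a does, however, presume that MAT days is such a variable.

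The comparison of Cox fits with and without MAT days is itself an inference. Section 10 assigns a survival analysis to the direct effect and multilevel SEM with REML to mediation, and never says that two Cox coefficients will be compared. This stands, but it leaves a gap in its place: the named model does not describe a censored outcome.

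The largest gaps need a small *a*, a large *b* and a substantial direct effect together. The protocol's only evidence on *a* points higher. The pilot reports 11.2 against 0.76 days of MAT (n = 16 and 17, p < .05). If that was a t-test, d is at least 2.04 × √(1/16 + 1/17) = 0.71. It is a 30-day figure, so the nine-month path may be smaller, but at a = .7 the error is 10 points or less. It is about nil if RIMO works wholly through MAT. The growth seen with no mediation needs a = 0, where joint significance would normally fail and no mediation would be declared.

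Finally, near-universal relapse is inferred from the definition and from expected use at contact; it is not stated. The Sobel loss arises only if both tests must pass, which section 10 does not say, and the planned bootstrap standard error makes the inequality in Step 6 approximate.

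**Conclusion.** The concern holds in a limited form. Section 10 applies one coefficient-reduction rule to a set of outcomes that includes a censored one, and gives no mediation model that fits it. Read on the Cox scale, the rule understates the mediated share of RIMO's effect on time to relapse. At about 90-95% relapse the understatement is about 0-10 points with a large *a* or little direct effect, and about 13-29 points with *a* of 0.2-0.3 SD and a direct log hazard ratio of -0.4. At 10-15% events it is small. All these figures rest on assumed path sizes and an assumed relapse rate.

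The harm is confined to the mediated share, the full/partial label and any test of how much the coefficient changed. Detection of mediation by joint significance is largely intact. The primary outcome, time to MAT initiation, is not touched. The change should be made, but it concerns a secondary, explanatory hypothesis.

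**What to change.** In section 10, for H2a only:

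- State the survival mediation model.
- Define the indirect effect either as the product a·b on a log-time (AFT) scale, or as a counterfactual indirect effect on relapse-free days over nine months.
- Base the decision on a bootstrap percentile interval for that effect, resampling participants.
- Do not use the coefficient-reduction or loss-of-significance rule for this outcome.
- State that the Sobel z is not an additional hurdle to joint significance.
- State the relapse proportion expected, so that the choice of scale can be judged.

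The cost is SAP wording, and bootstrapping is already planned. The downside is that the H2a mediation model would differ in form from the Cox model used for the total effect, and the report should say so. The change of scale does not settle time order: Table 2.1 totals MAT days over nine months, so some can fall after relapse. That needs its own treatment.

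### Section 10 pairs joint significance with a Sobel test for each indirect effect and names no deciding rule; if both must pass, the conservative Sobel test decides and power is lost when both paths are modest

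*Combined protocol and SAP*

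**What the plan says.** Indirect effects are stated hypotheses. H2 runs through MAT days. For H3, Section 1 states that "RIMO will have direct and indirect (via days of MAT treatment and days of opioid use) effects on" fatalities, OUD symptoms, physical health, mental health and health care cost.

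The paragraph on indirect effects in Section 10 names two tests in one sentence. The first is "joint-significance testing of the path" z-scores, which asks whether each path is significant. The second is attached to it: "with a Sobel test using a standard error based on bootstrapping and criteria of" p < .05, applied to how far the path coefficient changes. The plan does not say whether both tests must pass, whether either is enough, or which one governs. It specifies no confidence interval for the indirect effect.

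The same paragraph has a further rule for labelling the result: "Loss of statistical significance in the path coefficient from the intervention conditions to the other outcome variables would indicate full mediation", while a smaller coefficient means partial mediation.

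Section 4 adds: "For mediation analysis, the tests should also have 80%+ power for a 2-tailed test of" p < .05 and an indirect effect of d = .2 or more. It names neither the test nor the sizes of the two paths.

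**The concern.** Joint significance and the Sobel test are different tests of one quantity, the product a × b, where a is the path from RIMO to the mediator and b the path from mediator to outcome. Joint significance asks each path to pass on its own. Sobel divides the product by its standard error and compares the ratio with a normal curve. Near zero the product of two estimates is skewed, so that comparison is conservative. Taking the standard error from a bootstrap changes the denominator but not the reference curve.

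Two things are at stake. If the governing test is settled only after results are seen, one data set can be reported as showing mediation or as failing to show it. If both tests are required, the weaker one decides, and real indirect effects of modest size are missed more often than Section 4 suggests.

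**Working it through.** **Inputs.** From the documents: two-sided p < .05; 350 people, "randomized into two groups of 175 each"; effective n of 398 to 429 per group, taken as printed in Section 4; pilot MAT days of 11.2 against 0.76 with 16 and 17 people, p < .05 (Section 1). Assumed: path a for opioid days and every path b, which the documents do not give and which are therefore varied.

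**1. The plan's own figure.** The 80%+ mediation power cannot be reproduced without path sizes and a named test. The direct-effect claim beside it can: d = .2 with 398 per group gives 80.5% power (83.4% with 429). A path of that size has an expected z of 0.2 × √(398/2) = 2.82.

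**2. Thresholds.** Joint significance needs |za| > 1.96 and |zb| > 1.96. Sobel needs za·zb/√(za² + zb²) > 1.96.
- Equal paths: z/√2 > 1.96, so z must exceed 2.77. With za·zb/√(za² + zb² + 1), a proxy for a bootstrap standard error, it is 2.86.
- Both paths at 2.5: joint significance is met, but Sobel z = 2.5/√2 = 1.77, p = .077.
- Unequal paths: Sobel needs zb > 1.96·za/√(za² − 1.96²), which is 3.16 at za = 2.5, 2.13 at za = 5 and 2.00 at za = 10.

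**3. Direction of conflict.** For positive z's, za·zb/√(za² + zb²) is always below the smaller of the two. Sobel significance therefore implies joint significance. In 2,000,000 simulated pairs, none was Sobel-positive and joint-negative. With an actual bootstrap standard error this holds in practice rather than by algebra.

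**4. Independent normal path z's** (first-order Sobel / bootstrap-type proxy):
- Expected z 2.82 and 2.82: power 65% joint (0.805² = 0.648), 42% / 38% Sobel; conflict 23% / 27%.
- Expected z 2.82 and 5: conflict 7% / 8%.
- Expected z 2.82 and 8: conflict 2% / 2%.

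**5. Simulation with a real bootstrap standard error.** n = 350, one mediator, one value per person, ordinary least squares; 1,500 trials with 400 resamples. Expected z is d·√(175/2) = 9.35d for path a and about b·√350 = 18.7b for path b.

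| d for a | slope b | expected z (a, b) | joint | Sobel, bootstrap SE | percentile interval | joint and Sobel disagree |
|---|---|---|---|---|---|---|
| 0.2 | 0.2 | 1.9, 3.7 | 44.6% | 27.3% | 44.8% | 17.4% |
| 0.3 | 0.16 | 2.8, 3.0 | 67.9% | 42.1% | 66.9% | 25.9% |
| 0.3 | 0.2 | 2.8, 3.7 | 75.4% | 56.5% | 74.8% | 18.9% |
| 0.4 | 0.2 | 3.7, 3.7 | 92.7% | 81.9% | 92.4% | 11.1% |
| 0.3 | 0.3 | 2.8, 5.6 | 79.9% | 74.1% | 80.7% | 5.9% |
| 0.2 | 0.5 | 1.9, 9.4 | 47.5% | 45.4% | 48.3% | 2.5% |
| 0.4 | 0.5 | 3.7, 9.4 | 96.4% | 96.0% | 96.5% | 0.4% |

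At d = 0.2 and b = 0.15, repeat runs gave joint 36 to 39%, Sobel 14 to 16%, percentile 34 to 37%, and disagreement in 20 to 25%. At d = 0.8 and b = 0.15 (one strong path) they gave 79 to 81%, 77 to 79%, 80 to 82%, and disagreement in 4%.

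Relative loss from Sobel: (75.4 − 56.5)/75.4 = 25%; (67.9 − 42.1)/67.9 = 38%; at d = 0.2 and b = 0.15, (36 − 16)/36 = 56% to (39 − 14)/39 = 64%.

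**6. False positives.** With a = 0 and expected zb = 2.82, joint significance rejects in 4.0% and Sobel in 1.0% (0.8% bootstrap-type). In the bootstrap simulation with a = 0 and b = 0.3 the rates are 5.1% joint, 3.5% Sobel and 5.2% percentile. The last is within simulation error of 5%: √(0.05 × 0.95/1,500) = 0.6 points.

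**7. MAT days.** Pilot p < .05 with 33 people means |t| of at least 2.04. If that effect held at n = 350, za would be at least 2.04 × √(350/33) = 6.6, and Sobel would need zb of only about 2.05. The pilot covered 30 days, so this is an assumption.

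**The case against.** The strongest reply is about effect size. Section 4 plans for an indirect effect of d = .2. If that means a × b = 0.2, every split tried in a single-level simulation (for example d = .3 with b = .67, or d = .8 with b = .25) gave disagreement below 1%. The weakest modest case above has a × b = 0.2 × 0.15 = 0.03, far smaller. This stands, and it limits the size of the problem. It does not supply the missing rule, and reading d = .2 as a × b is itself an interpretation.

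A second reply is that the sentence already resolves itself: joint significance accompanied by Sobel, with the p-value attached to the degree of change, means both must pass. That is a natural reading, but under it Sobel decides, which is the reading that costs power.

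Third, joint significance performs as well as the percentile interval in these simulations, so the interval may look like preference. On power that is fair, and naming joint significance alone would also end the ambiguity. It would not give an interval for the size of the indirect effect, whereas the planned bootstrap draws can.

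Fourth, the simulations use one value per person and least squares, not the planned multilevel structural equation model with repeated observations. The percentages show scale and are not this trial's error rates.

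**Conclusion.** The point holds in limited form. Section 10 names two tests and no governing rule, and the reading that requires both hands the decision to the conservative test. When both paths are modest, the tests disagree in about 20 to 25% of simulated trials (17 to 26% across the cases shown), and Sobel power is a quarter to over a half lower. With one strong path (expected z of about 7 or more) or a × b near 0.2, disagreement is about 4% or less. These figures rest on assumed path sizes and a single-level model.

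Four stronger inferences are not supported:
- That the tests contradict each other in both directions or over most results. Conflict runs one way, and a non-significant Sobel result does not refute mediation.
- That the plan reports a faulty Sobel interval. It specifies a p-value and no interval.
- That false positives are inflated. Sobel rejects too seldom.
- That H3 conclusions through opioid days will turn on the choice. Section 4 gives d = .2 as a detectable direct effect, not as the expected RIMO effect on opioid days, and a strong link from opioid days to an outcome such as OUD symptoms would make conflict rare.

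These are secondary mechanism analyses; the primary outcome, time to starting MAT, is unaffected. The change should be made because it is cheap.

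**What to change.** Drop the Sobel test and pre-specify one deciding rule, for example:

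> *Each indirect effect (a × b) will be estimated with a 95% percentile bootstrap confidence interval, resampling participants. Mediation is concluded if the interval excludes zero. Where the model estimator, multiple imputation, or the time-to-relapse and fatality models do not allow this, a 95% Monte Carlo (distribution-of-the-product) interval from the path estimates and standard errors, pooled over imputations where relevant, decides instead. Joint significance of the paths is descriptive only.*

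For this to be the only deciding rule, the full and partial mediation labels in the same paragraph should be marked as descriptive. Section 4 could then state mediation power for this test with explicit a and b.

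Cost: slightly more analysis work and a short added rule for imputed data and non-continuous outcomes. Bootstrapping is already planned and no new data are needed.
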